# 7 Assessment of Safety

An **adverse event** (AE) is any symptom, sign, illness or experience that develops or worsens in severity during the course of the study. Intercurrent illnesses or injuries should be regarded as adverse events. Abnormal results of diagnostic procedures are considered to be adverse events if the abnormality:

- results in study withdrawal
- is associated with a serious adverse event
- is associated with clinical signs or symptoms
- leads to additional treatment or to further diagnostic tests
- is considered by the investigator to be of clinical significance

## 7.1 Definition of Adverse Events (AE)

### Serious Adverse Event

Adverse events are classified as serious or non-serious. A **serious adverse event** is any AE that is:

- fatal
- life-threatening
- requires or prolongs hospital stay
- results in persistent or significant disability or incapacity
- a congenital anomaly or birth defect
- an important medical event

Important medical events are those that may not be immediately life threatening but are clearly of major clinical significance. They may jeopardize the subject and may require intervention to prevent one of the other serious outcomes noted above. For example, drug overdose or abuse, a seizure that did not result in in-patient hospitalization, or intensive treatment of bronchospasm in an emergency department would typically be considered serious.

All adverse events that do not meet any of the criteria for serious should be regarded as **non-serious adverse events**.

## 7.2 Definition of Unanticipated Problems (UP)

### Unanticipated Problems Involving Risk to Subjects or Others

Any incident, experience, or outcome that meets all of the following criteria:

- Unexpected in nature, severity, or frequency (i.e., not described in study-related documents such as the IRB-approved protocol or consent form, the investigators brochure, etc)
- Related or possibly related to participation in the research (i.e., possibly related means there is a reasonable possibility that the incident experience, or outcome may have been caused by the procedures involved in the research)
- Suggests that the research places subjects or others at greater risk of harm (including physical, psychological, economic, or social harm).

CONFIDENTIAL

This material is the property of the NYU School of Medicine and Langone Medical Center. Do not disclose or use except as authorized in writing by the study sponsor

This definition could include an unanticipated adverse device effect, any serious adverse effect on health or safety or any life-threatening problem or death caused by, or associated with, a device, if that effect, problem, or death was not previously identified in nature, severity, or degree of incidence in the investigational plan or application (including a supplementary plan or application), or any other unanticipated serious problem associated with a device that relates to the rights, safety, or welfare of subjects (21 CFR 812.3(s)).

## 7.3 Classification of an Adverse Event

### 7.3.1 Severity of Event

For AEs not included in the protocol defined grading system, the following guidelines will be used to describe severity.

- **Mild** – Events require minimal or no treatment and do not interfere with the participant’s daily activities.
- **Moderate** – Events result in a low level of inconvenience or concern with the therapeutic measures. Moderate events may cause some interference with functioning.
- **Severe** – Events interrupt a participant’s usual daily activity and may require systemic drug therapy or other treatment. Severe events are usually potentially life-threatening or incapacitating.

### 7.3.2 Relationship to Study Agent

*The clinician’s assessment of an AE’s relationship to study agent (drug, biologic, device) is part of the documentation process, but it is not a factor in determining what is or is not reported in the study. If there is any doubt as to whether a clinical observation is an AE, the event should be reported. All AEs must have their relationship to study agent assessed. In a clinical trial, the study product must always be suspect. To help assess, the following guidelines are used.*

1. **Related** – *The AE is known to occur with the study agent, there is a reasonable possibility that the study agent caused the AE, or there is a temporal relationship between the study agent and event. Reasonable possibility means that there is evidence to suggest a causal relationship between the study agent and the AE.*
2. **Not Related** – *There is not a reasonable possibility that the administration of the study agent caused the event, there is no temporal relationship between the study agent and event onset, or an alternate etiology has been established.*

*For all collected AEs, the clinician who examines and evaluates the participant will determine the AE’s causality based on temporal relationship and his/her clinical judgment. The degree of certainty about causality will be graded using the categories below.*

1. **Definitely Related** – *There is clear evidence to suggest a causal relationship, and other possible contributing factors can be ruled out. The clinical event, including an abnormal laboratory test result, occurs in a plausible time relationship to drug administration and cannot be explained by concurrent disease or other drugs or chemicals. The response to withdrawal of the drug (dechallenge) should be clinically plausible. The event must be pharmacologically or phenomenologically definitive, with use of a satisfactory rechallenge procedure if necessary.*
2. **Probably Related** – *There is evidence to suggest a causal relationship, and the influence of other factors is unlikely. The clinical event, including an abnormal laboratory test result, occurs within a reasonable time after administration of the drug, is unlikely to be attributed to concurrent disease or other drugs or chemicals, and follows a clinically reasonable response on withdrawal (dechallenge). Rechallenge information is not required to fulfill this definition.*
3. **Possibly Related** – *There is some evidence to suggest a causal relationship (e.g., the event occurred within a reasonable time after administration of the trial medication). However, other factors may have contributed*

CONFIDENTIAL

This material is the property of the NYU School of Medicine and Langone Medical Center. Do not disclose or use except as authorized in writing by the study sponsor

to the event (e.g., the participant's clinical condition, other concomitant events). Although an AE may rate only as "possibly related" soon after discovery, it can be flagged as requiring more information and later be upgraded to "probably related" or "definitely related," as appropriate.

4. **Unlikely to be related** – A clinical event, including an abnormal laboratory test result, whose temporal relationship to drug administration makes a causal relationship improbable (e.g., the event did not occur within a reasonable time after administration of the trial medication) and in which other drugs or chemicals or underlying disease provides plausible explanations (e.g., the participant's clinical condition, other concomitant treatments).
5. **Not Related** – The AE is completely independent of study drug administration, and/or evidence exists that the event is definitely related to another etiology. There must be an alternative, definitive etiology documented by the clinician.

### 7.3.3 Expectedness

The PI, [name], will be responsible for determining whether an AE is expected or unexpected. An AE will be considered unexpected if the nature, severity, or frequency of the event is not consistent with the risk information previously described for the study agent.

### 7.4 Time Period and Frequency for Event Assessment and Follow-Up

The occurrence of an AE or SAE may come to the attention of study personnel during study visits and interviews of a study participant presenting for medical care, or upon review by a study monitor. All AEs including local and systemic reactions not meeting the criteria for SAEs will be captured on the appropriate RF. Information to be collected includes event description, time of onset, clinician's assessment of severity, relationship to study product (assessed only by those with the training and authority to make a diagnosis), and time of resolution/stabilization of the event. All AEs occurring while on study must be documented appropriately regardless of relationship. All AEs will be followed to adequate resolution.

Any medical condition that is present at the time that the participant is screened will be considered as baseline and not reported as an AE. However, if the study participant's condition deteriorates at any time during the study, it will be recorded as an AE. UPs will be recorded in the data collection system throughout the study.

Changes in the severity of an AE will be documented to allow an assessment of the duration of the event at each level of severity to be performed. AEs characterized as intermittent require documentation of onset and duration of each episode.

The PI will record all reportable events with start dates occurring any time after informed consent is obtained until 7 (for non-serious AEs) or 30 days (for SAEs) after the last day of study participation. At each study visit, the investigator will inquire about the occurrence of AE/SAEs since the last visit. Events will be followed for outcome information until resolution or stabilization.

All unresolved adverse events should be followed by the investigator until the events are resolved, the subject is lost to follow-up, or the adverse event is otherwise explained. At the last scheduled visit, the investigator should instruct each subject to report any subsequent event(s) that the subject, or the subject's personal physician, believes might reasonably be related to participation in this study. The investigator should notify the study sponsor of any death or adverse event occurring at any time after a subject has discontinued or terminated study participation that may reasonably be related to this study. The sponsor should also be notified if the investigator should become aware of the development of cancer or of a congenital anomaly in a subsequently conceived offspring of a subject that has participated in this study.

## **7.5 Reporting Procedures – Notifying the IRB**

### **7.5.1 Unanticipated Problem Reporting**

Incidents or events that meet the OHRP criteria for UPs require the creation and completion of an UP report form. It is the site investigator's responsibility to report UPs to their IRB. The UP report will include the following information:

1. Protocol identifying information: protocol title and number, PI's name, and the IRB project number;
2. A detailed description of the event, incident, experience, or outcome;
3. An explanation of the basis for determining that the event, incident, experience, or outcome represents an UP;
4. A description of any changes to the protocol or other corrective actions that have been taken or are proposed in response to the UP.

To satisfy the requirement for prompt reporting, UPs will be reported using the following timeline:

- UPs that are SAEs will be reported to the IRB within 7 days of the investigator becoming aware of the event.
- Any other UP will be reported to the IRB within 7 days of the investigator becoming aware of the problem.
- All UPs should be reported to appropriate institutional officials (as required by an institution's written reporting procedures), the supporting agency head (or designee), and OHRP within 7 days of the IR's receipt of the report of the problem from the investigator.

## **7.6 Safety Oversight**

It is the responsibility of the Principal Investigator, and co-investigator, [name] to oversee the safety of the study at his/her site. This safety monitoring will include careful assessment and appropriate reporting of adverse events as noted above, as well as the construction and implementation of a site data and safety-monitoring plan. Adverse Events such as development of an allergy to local anesthetic, inadvertent intravascular injection of local anesthetic and infection at site of injection will be reviewed every three months. Serious adverse events are rare and are unlikely to occur but if a serious adverse event occurs, steps will be taken to address it. Study recruitment will cease temporarily while a data safety monitoring team convenes to review the event. Medical monitoring will include a regular assessment of the number and type of serious adverse events.

## **8 Source Documents and Access to Source Data/Documents**

Source data is all information, original records of clinical findings, observations, or other activities in a clinical trial necessary for the reconstruction and evaluation of the trial. Source data are contained in source documents. Examples of these original documents, and data records include: hospital records, clinical and office charts, laboratory notes, memoranda, subjects' diaries or evaluation checklists, pharmacy dispensing records, recorded data from automated instruments, copies or transcriptions certified after verification as being accurate and complete, microfiches, photographic negatives, microfilm or magnetic media, x-rays, subject files, and records kept at the pharmacy, at the laboratories, and at medico-technical departments involved in the clinical trial. It is acceptable to use CRFs as source documents. If this is the case, it should be stated in this section what data will be collected on CRFs and what data will be collected from other sources.

The study case report form (CRF) is the primary data collection instrument for the study. All data requested on the CRF must be recorded. All missing data must be explained. If a space on the CRF is left blank because the procedure was not done or the question was not asked, write "N/D". If the item is not applicable to the individual case, write "N/A". All entries should be printed legibly in black ink. If any entry error has been made, to correct

CONFIDENTIAL

This material is the property of the NYU School of Medicine and Langone Medical Center. Do not disclose or use except as authorized in writing by the study sponsor

such an error, draw a single straight line through the incorrect entry and enter the correct data above it. All such changes must be initialed and dated. DO NOT ERASE OR WHITE OUT ERRORS. For clarification of illegible or uncertain entries, print the clarification above the item, then initial and date it.

Access to study records will be limited to IRB-approved members of the study team. The investigator will permit study-related monitoring, audits, and inspections by the IRB/EC, the sponsor, government regulatory bodies, and University compliance and quality assurance groups of all study related documents (e.g. source documents, regulatory documents, data collection instruments, study data etc.). The investigator will ensure the capability for inspections of applicable study-related facilities (e.g. pharmacy, diagnostic laboratory, etc.).

Participation as an investigator in this study implies acceptance of potential inspection by government regulatory authorities and applicable University compliance and quality assurance offices.

## **9 Quality Assurance and Quality Control**

QC procedures will be implemented beginning with the data entry system and data QC checks that will be run on the database will be generated. Any missing data or data anomalies will be communicated to the site(s) for clarification/resolution.

Following written SOPs, the monitors will verify that the clinical trial is conducted and data are generated, documented (recorded), and reported in compliance with the protocol, GCP, and the applicable regulatory requirements (e.g., Good Laboratory Practices (GLP), Good Manufacturing Practices (GMP)).

The investigational site will provide direct access to all trial related sites, source data/documents, and reports for the purpose of monitoring and auditing by the sponsor, and inspection by local and regulatory authorities.

## **10 Ethics/Protection of Human Subjects**

### ***10.1 Ethical Standard***

The investigator will ensure that this study is conducted in full conformity with Regulations for the Protection of Human Subjects of Research codified in 45 CFR Part 46, 21 CFR Part 50, 21 CFR Part 56, and/or the ICH E6.

### ***10.2 Institutional Review Board***

The protocol, informed consent form(s), recruitment materials, and all participant materials will be submitted to the IRB for review and approval. Approval of both the protocol and the consent form must be obtained before any participant is enrolled. Any amendment to the protocol will require review and approval by the IRB before the changes are implemented to the study. All changes to the consent form will be IRB approved; a determination will be made regarding whether previously consented participants need to be re-consented.

### ***10.3 Participant and Data Confidentiality***

Information about study subjects will be kept confidential and managed according to the requirements of the Health Insurance Portability and Accountability Act of 1996 (HIPAA). Those regulations require a signed subject authorization informing the subject of the following:

- What protected health information (PHI) will be collected from subjects in this study
- Who will have access to that information and why
- Who will use or disclose that information
- The rights of a research subject to revoke their authorization for use of their PHI.

In the event that a subject revokes authorization to collect or use PHI, the investigator, by regulation, retains the ability to use all information collected prior to the revocation of subject authorization. For subjects that have revoked authorization to collect or use PHI, attempts should be made to obtain permission to collect at least vital status (i.e. that the subject is alive) at the end of their scheduled study period.

CONFIDENTIAL

This material is the property of the NYU School of Medicine and Langone Medical Center. Do not disclose or use except as authorized in writing by the study sponsor

Participant confidentiality is strictly held in trust by the participating investigators, their staff, and the sponsor(s) and their agents. Therefore, the study protocol, documentation, data, and all other information generated will be held in strict confidence. No information concerning the study or the data will be released to any unauthorized third party without prior written approval of the sponsor.

The study monitor, other authorized representatives of the sponsor, representatives of the IRB or pharmaceutical company supplying study product may inspect all documents and records required to be maintained by the investigator, including but not limited to, medical records (office, clinic, or hospital) and pharmacy records for the participants in this study. The clinical study site will permit access to such records.

The study participant's contact information will be securely stored at each clinical site for internal use during the study. At the end of the study, all records will continue to be kept in a secure location for as long a period as dictated by local IRB and Institutional regulations.

Study participant research data, which is for purposes of statistical analysis and scientific reporting, will be transmitted to and stored at NYU Langone Medical Center. This will not include the participant's contact or identifying information. Rather, individual participants and their research data will be identified by a unique study identification number. The study data entry and study management systems used by clinical sites and by NYU Langone Medical Center research staff will be secured and password protected. At the end of the study, all study databases will be de-identified and archived at the NYU Langone Medical Center.

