### **3.6 Total Number of Participants and Sites**

Recruitment will end when 160 participants have been enrolled. It is expected that there will be subjects enrolled who will be lost to follow up and be evaluated by intention-to-treat. The sites for enrollment will be the NYU Langone Orthopedic Hospital and NYU Ambulatory Surgery Center at 38th street.

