### **3.7 Participant Withdrawal or Termination**

Participants are free to withdraw from participation in the study at any time upon request. An investigator may terminate participation in the study if:

1. Any clinical adverse event (AE), laboratory abnormality, or other medical condition or situation occurs such that continued participation in the study would not be in the best interest of the participant
2. The participant meets an exclusion criterion (either newly developed or not previously recognized) that precludes further study participation

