#### **4.2.4 Withdrawal/Early Termination Visit**

Subjects may discontinue their participation in the study at any time. As there is only a single intervention, and the safety of this is not in question, further follow up will not be required if a subject decides to terminate their participation in the study.

CONFIDENTIAL

This material is the property of the NYU School of Medicine and Langone Medical Center. Do not disclose or use except as authorized in writing by the study sponsor

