## 6 Statistical Analysis

### 6.1 General Approach

The primary analysis will follow the intention-to-treat (ITT) principle in order to evaluate the true outcome of the intervention as experienced by the patient who is blinded to the intervention.

Continuous and categorical baseline characteristics will be compared using Hedges standardized difference

Normally distributed data will be compared using t tests while non-normally distributed continuous outcomes will be assessed using the Mann-Whitney U test.

It is anticipated that the data for some subjects will be incomplete for various reasons: missing daily-diary entries, refusal to answer a question on the questionnaire, onset of illness, loss-to-follow-up, etc. All occurrences of incomplete data will be investigated to carefully document the reasons for the missing data. If the primary outcome (amount of opioid utilization for the first 24 hours after surgery) cannot be ascertained with a reasonable degree of certainty, the patient will be excluded from the data analysis.

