### 6.2 Analysis of Endpoints

#### Primary Endpoints:

1. Opioid utilization for the first 24 hours after surgery, including during surgery, calculated as oxycodone equivalent.

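### The protocol does not ask for the 24-hour opioid total once participation ends, so patients who stop before the POD 1 report can drop out of the ITT primary comparison

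*Combined protocol and SAP*

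**What the plan says.** All references are to the combined protocol and SAP.

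- **Primary endpoint (6.2):** "Opioid utilization for the first 24 hours after surgery, including during surgery, calculated as oxycodone equivalent". PACU opioid use is taken from EPIC (2.1), opioid use is recorded on the day of surgery (4.2.2), and home use comes from the POD 1 and POD 3 phone calls (2.1, 4.2.3).
- **Subject ends participation (4.2.4):** "further follow up will not be required if a subject decides to terminate their participation in the study". The reason given is that there is one intervention and its safety is not in doubt.
- **Investigator ends participation (3.7):** "An investigator may terminate participation in the study if" an adverse event, other medical condition or exclusion criterion applies. Nothing is said about collecting outcomes afterwards.
- **Subject revokes authorization to use health information (10.3):** the investigator "retains the ability to use all information collected prior to the revocation of subject authorization", and "attempts should be made to obtain permission to collect at least vital status (i.e. that the subject is alive" at the end of the scheduled study period.
- **Analysis (6.1 and 3.6):** "The primary analysis will follow the intention-to-treat (ITT) principle", but if the primary outcome "cannot be ascertained with a reasonable degree of certainty, the patient will be excluded from the data analysis". Section 3.6 expects that "there will be subjects enrolled who will be lost to follow up and be evaluated by intention-to-treat", without saying how.

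**The concern.** The rationale in 4.2.4 is about safety. It does not consider that the same patients carry the efficacy outcome. Read together with the exclusion rule in 6.1, a patient who stops on the first day, before home tablets are reported, can be left out of the primary comparison even though obtaining the total would take little: doses already charted in hospital and one answer on a call the protocol already schedules. Staff are not told to ask.

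The loss may be informative. Someone who stops on the first day may do so because of poor pain control or opioid side effects, and either is related to the 24-hour total. If this happens more often in one arm, the complete-case difference is biased. An analysis method chosen later can model the missing totals, but it cannot replace values that could have been requested at the time.

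**Working it through.** **1. Which patients are affected.**

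| When participation ends | In-hospital doses | Home use to 24 h | Primary outcome |
|---|---|---|---|
| After the POD 1 report of home use | held | held | complete |
| After PACU, before the POD 1 report | held | not requested | at risk |
| Before or during PACU | partly held | not requested | at risk |

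The gap is therefore mainly home use up to 24 hours, in patients who stop before reporting it.

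**2. The plan's own sample size (6.3).** Inputs: means 25 and 32 mg (difference 7 mg), common SD 13 mg, two-sided alpha 0.05, power 0.90.

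Normal approximation: n = 2 × (1.960 + 1.282)² × (13/7)² = 2 × 10.51 × 3.449 = 72.5, so 73 per group. The noncentral t gives 73.45, so 74. The stated 72 is reproduced to within two patients.

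**3. Power if early withdrawals are excluded.** The documents give no dropout rate, so the range is assumed. Noncentral t, difference 7 mg, SD 13 mg:

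| Loss in each arm | Analysed per arm | Power |
|---|---|---|
| 0% | 80 | 0.923 |
| 5% | 76 | 0.910 |
| 10% | 72 | 0.894 |
| 15% | 68 | 0.876 |
| 20% | 64 | 0.856 |

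The 80 per arm absorbs a 10% loss exactly (72/0.9 = 80).

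**4. Bias from selective loss.** Suppose a fraction p of an arm is excluded and those patients' true totals average d above the full-arm mean. The mean of those remaining is then too low by d × p/(1 − p).

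Assume p = 0.10 in one arm and 0.05 in the other, with d = 6.5 mg (0.5 SD) or 13 mg (1 SD) in both:

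- d = 6.5: 6.5 × (0.1111 − 0.0526) = 0.722 − 0.342 = 0.38 mg, or 0.38/7 = 5% of the planned difference.
- d = 13: 13 × (0.1111 − 0.0526) = 1.444 − 0.684 = 0.76 mg, or 0.76/7 = 11%.
- Equal p and equal d in both arms: the two terms cancel and the shift is zero.

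If the infiltration arm loses more, the observed difference shrinks from 7 mg to between 6.2 and 6.6 mg. If the Pecs II arm loses more, it grows to between 7.4 and 7.8 mg.

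For scale, the standard error of the difference with 80 per arm is 13 × √(2/80) = 2.06 mg, so the shift is 0.18 to 0.37 standard errors.

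**The case against.** The strongest reply is that the text is permissive and the effect small. Section 4.2.4 does not forbid follow-up; 6.1 has incomplete data investigated and excludes a patient only when the total cannot be established; patients are blinded (2.1), which makes differential withdrawal less likely; the sample size already allows for dropout; and every rate in the bias calculation is assumed. All of this stands, and it limits the size of the point. It does not remove it. Not required leaves collection to the discretion of whoever is on duty, 6.1 asks staff to document why data are missing and not to recover them, and blinding does not stop a patient from leaving because of pain that differs by arm.

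A reader might go further than the documents allow in four ways:

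- *That 10.3 limits the request to vital status.* It sets vital status as a minimum. The valid criticism is only that it does not name the primary outcome.
- *That 10.3 and 4.2.4 contradict each other.* They cover different events, revoking authorization and ending participation. After revocation any further collection needs fresh permission, so loss there is not simply careless.
- *That vital status is useless here.* Death is a serious adverse event (7.1), and serious events are recorded until 30 days after participation (7.4). The request has a safety use and should stay.
- *That withdrawal can only mean stopping data collection, because the treatment is given once.* The envelope is opened after consent and before the intervention (2.1, 4.2.2), so a patient can leave after randomization and before receiving the assigned technique.

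**Conclusion.** The point holds in a limited form. Followed as written, 4.2.4 and 6.1 let patients who stop before the POD 1 report leave a comparison declared intention-to-treat, and 3.7 leaves the same gap for those whose participation the investigator ends. Not every withdrawal loses the outcome: 10.3 keeps data collected before revocation, no stricter rule appears for simply ending participation, and a patient who leaves after the 24-hour total is reported loses nothing.

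The likely effect is modest: well under half a standard error in the illustration, in either direction. That figure depends on unequal withdrawal and on withdrawers using more opioid than their arm's average, neither of which the documents inform. Loss of power is a minor matter. The reason to act is that the loss is possibly informative and often avoidable at very little cost.

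**What to change.** - **4.2.4:** separate stopping participation from refusing further data collection. Ask the participant two distinct questions, whether (a) chart review to 24 hours after surgery and (b) the POD 1 call may still go ahead, and record each answer.
- **3.7:** apply the same two questions when the investigator ends participation.
- **6.1:** state that participants whose 24-hour total is obtained this way are analysed in their assigned arm.
- **10.3:** add opioid use to 24 hours to the permission request made after revocation, and keep the vital status request.

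The cost is a few sentences with matching consent wording, and one short exchange with a patient who is leaving and may refuse. No visit or call is added. The change reduces the number of missing totals. It does not settle how the rest are analysed, since the exclusion rule in 6.1 would still apply to those who refuse.
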